6.7. Concomitant Therapy

All medications will be coded to the generic preferred name according to the current World Health Organization drug dictionary. All concomitant medications will be summarized by number and percentage of participants for the safety population using the base name (without esters or salts).

6.8. Primary and Secondary Biomarker Analyses

The primary and secondary biomarker analyses will be performed based on the BE population for each biomarker.

Change in ER expression is defined as the change from the pre-treatment to on-treatment sample. The geometric mean of change in the ER H-score, the percent change in H-score of ER expression, and the 90% CI (based on t statistic) will be summarized for each cohort.

Change in Ki-67 index is defined as the change from the pre-treatment to on-treatment. The geometric mean of change in Ki-67 expressing positive cells, the percent change in Ki-67 expressing positive cells, and its 90% CI (based on t statistic) will be summarized for each cohort. Subgroup analyses will be performed in participants with higher (>5%) baseline Ki-67%.

Change in PR expression is defined as the change from the pre-treatment to on-treatment. The geometric mean of change in the PR H-score, the percent change in H-score of PR expression, and the 90% CI (based on t statistic) will be summarized for each cohort.

Primary analysis of these variables (i.e. change from baseline for each biomarker) will utilize a linear model with arm and tumor histology as covariates, as below:

$$Y_{ijk} = \mu + \alpha_i + \beta_j + \varepsilon_{ijk}$$

where Y_{ijk} is the log ratio of each biomarker value at the on-treatment time point to the value at the pre-treatment time point for patient k in arm i with tumor histology status j . Least square mean (LSM) estimates and standard errors for each arm will be derived from this model.

LSM estimates and CIs will need to be back transformed to the geometric mean scale. Letting $\hat{\mu}$ denote LSM estimate, the geometric mean change and geometric mean percent change will be calculated as $\exp(\hat{\mu})$ and $100\%(\exp(\hat{\mu})-1)$, respectively.

For each of the biomarkers above, not only the geometric mean change from baseline and percent change will be reported, the medians, ranges and geometric means for the pre-treatment and on-treatment results will also be reported. A plot of change in the biomarker values will also be provided.

Subgroup analysis for each of the biomarker endpoints by the stratification factor (i.e. tumor histology) may also be conducted if deemed appropriate.

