4.1. Overall Design

Study EMBER-2 is a Phase 1, open-label, randomized, pre-operative window study of LY3484356 in post-menopausal women with Stage I to III ER+, HER2- breast cancer who are scheduled for surgery with curative intent. Patients will consent to provide tumor samples obtained at the time of diagnosis and at the time of scheduled surgery or repeat biopsy, for the purpose of biomarker analyses. Patients will then be randomized to either 400 or 800 mg LY3484356 or directly assigned to the 200 mg dose (see table in Section 6.1) and receive LY3484356 for 15 days, up to and including the day of scheduled surgery or repeat biopsy (if neoadjuvant therapy is subsequently planned). Tumor samples taken pre- and on-treatment with LY3484356, at the time of diagnosis and scheduled surgery/repeat biopsy, respectively, will then be evaluated for biologic effects, as outlined in the study objectives. (See Section 8.8 for specifics regarding tumor tissue collections).

For the 400 and 800 mg doses, randomization will be stratified by tumor histology (infiltrating ductal carcinoma [IDC] versus infiltrating lobular carcinoma [ILC]; as locally determined from the diagnostic tumor biopsy). No stratification will occur for the 200 mg dose level.

A treatment window of 15 days (-2 to +7 days [ie, a range of 13 to 22 days of LY3484356 treatment] will be permissible to facilitate flexibility in scheduling of the on-treatment surgery/biopsy. The last dose of LY3484356 will be taken on the morning of surgery/biopsy.

The primary endpoint for this study is to determine change in ER expression (between pre- and on-treatment tumor samples) following LY3484356 treatment at each dose level. These changes will be measured utilizing an immunohistochemistry (IHC) H-score (0 to 300) that captures the change in the number of positive cells and intensity of ER staining.

Secondary endpoints include assessment of change in PR expression by IHC H-score (0 to 300); change in the percentage of Ki-67 staining positive tumor cells (Ki-67 index); and safety and tolerability and PK evaluation of LY3484356.

Taken together, these data will be used to describe the comparative biologic effects of each dose level of LY3484356 on early stage, treatment naïve ER+ breast tumors.

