5.2. Determination of Sample Size

Approximately **30** participants will be assigned equally to the different dose-level cohorts in this study to ensure that conservatively 20 participants, with evaluable biomarker data are ultimately

available for analysis from each cohort. The sponsor may elect to continue accrual until sufficient biomarker data is generated.

The sample size of 20 participants per cohort provides a 90% tolerance probability that the 2-sided 90% confidence interval (CI) for geometric mean of change from baseline in ER expression for each cohort will extend no more than 0.34 from the observed geometric mean in logarithm scale, assuming that the true standard deviation is 0.74 (Kuter et al. 2012) and that the CI is based on the t statistic.

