6.2. Adjustments for Covariates

The stratification factor used in randomization is considered important prognostic factors and are thought to be associated with outcomes. Subgroup analyses based on the stratification factor will be conducted if appropriate.

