6.5.2. Baseline Disease Characteristics

Disease characteristics will be summarized. Disease characteristics will include the following:

- Initial pathological diagnosis
- Disease stage (Stage IIA, Stage IIB, etc.) at study entry
- Histopathological diagnosis grade (G1, G2, etc.) at study entry
- Baseline Eastern Cooperative Oncology Group (ECOG) performance status (PS)
- HER2 status (negative/positive)
- Progesterone receptor status (negative/positive)
- Estrogen receptor status (negative/positive)
- Baseline ER expression, Ki-67 index, and PR expression

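### The primary biomarker model omits the patient's own baseline value; the analysis is valid, but comparisons across doses lose some precision

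*SAP*

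**What the plan says.** SAP 6.8 states that the primary analysis of each biomarker "will utilize a linear model with arm and tumor histology as covariates". The response "is the log ratio of each biomarker value at the on-treatment time point to the value at the pre-treatment time point". The SAP continues: "Least square mean (LSM) estimates and standard errors for each arm will be derived from this model". These estimates are then exponentiated to geometric mean ratios and percent changes. The model equation has an intercept, an arm effect, a histology effect and an error, and nothing else.

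No other section supplies a baseline term. SAP 6.2 mentions only the stratification factor and adds: "Subgroup analyses based on the stratification factor will be conducted if appropriate". Protocol 9.4.2 and 9.4.3 give per-cohort geometric means with 90% CIs and name no covariates.

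Baseline biomarker values are used descriptively. SAP 6.5.2 lists "Baseline ER expression, Ki-67 index, and PR expression" among the characteristics to be summarised, and SAP 6.8 says that "the medians, ranges and geometric means for the pre-treatment and on-treatment results will also be reported". Ki-67 also has a subgroup with baseline above 5%. SAP 6.1.1 defines the biomarker-evaluable population by a valid result both before and on treatment, so the baseline value is never missing in the analysed set.

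On design, Protocol 6.3 randomises 400 and 800 mg 1:1 and opens the 200 mg cohort only after those two close. Protocol 4.1 adds: "No stratification will occur for the 200 mg dose level". Protocol 2.1 and 4.1 say that the doses will be compared, and Protocol 9.1 rules out formal testing.

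**The concern.** A log ratio subtracts log baseline with a coefficient fixed at 1. If the true slope of log(on-treatment) on log(pre-treatment) is not 1, the log ratio still depends on where the patient started. That dependence then sits in the residual. It widens the intervals, and a baseline gap between cohorts moves the difference between doses by (slope − 1) times the gap.

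The documents give some reason to expect a slope other than 1. Pre-treatment tissue is a biopsy, possibly archival and up to 6 weeks old at consent, while on-treatment tissue may be a surgical resection (Protocol 8.8). The H-score is also bounded at 0 and 300 (Protocol 4.1).

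At stake is how clearly the doses can be told apart with about 20 evaluable patients each. The covariate is already collected and complete. Any patient whose log ratio can be computed also has a computable log baseline, so no patient would be lost by adding it.

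**Working it through.** **1. The plan's own precision figure.** SAP 5.2 uses n = 20 per cohort, SD 0.74 on the log scale, a two-sided 90% CI and 90% tolerance probability. Half-width = t(0.95, 19) × 0.74 × √(χ²(0.90, 19)/19) / √20 = 1.729 × 0.74 × √(27.20/19) / 4.472 = 0.342. This agrees with the stated 0.34. The sample-size statement is sound and is not in question.

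**2. Effect of adding log baseline.** Let r be the within-arm correlation of the log ratio with log baseline. It is assumed here, because the documents do not give it. The residual SD becomes 0.74√(1 − r²). With three cohorts of 20 and two histology levels (SAP 5.3), the residual df go from 60 − 3 − 1 = 56 to 55. The 90% half-widths for a between-dose difference are:

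- planned model: 1.6725 × 0.74 × √(2/20) = 0.391
- with log baseline: 1.6730 × 0.74√(1 − r²) × √[(2/20)(1 + 1/54)], where 1/54 is the average cost of estimating the extra slope.

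The SE of a single dose's least square mean, taken at the common mean log baseline, is 0.74√[(1 − r² + r²/3)/20].

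| \|r\| | residual SD | half-width of difference | change from 0.391 | SE of one dose mean |
|---|---|---|---|---|
| 0 | 0.740 | 0.395 | 1% wider | 0.166 |
| 0.3 | 0.706 | 0.377 | 4% narrower | 0.160 |
| 0.5 | 0.641 | 0.342 | 13% narrower | 0.151 |
| 0.7 | 0.528 | 0.282 | 28% narrower | 0.136 |

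Break-even lies a little below |r| = 0.2. The percentages do not depend on the 0.74, so they apply equally to PR and Ki-67. A simulation of the two models (20,000 runs) agrees: the SD of the difference fell from 0.235 to 0.205 at r = 0.5 and from 0.238 to 0.171 at r = 0.7.

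**3. What is plausible for ER.** Inclusion criterion 2c requires more than 50% positive nuclei, or an Allred score above 5. On the first route the H-score lies roughly between 50 and 300. The largest possible log-SD is then ln(6)/2 = 0.90, and a log-uniform spread gives ln(6)/√12 = 0.52. I take a baseline log-SD s of 0.30 to 0.52, hold the log-ratio SD at 0.74, and let ρ be the pre/on-treatment correlation. Then the on-treatment log-SD is p = ρs + √(0.74² − s²(1 − ρ²)), and r = (ρp − s)/0.74. Putting r into step 2:

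| s | ρ = 0.3 | ρ = 0.5 | ρ = 0.7 |
|---|---|---|---|
| 0.30 | r = −0.09, <1% wider | r = 0.16, <1% narrower | r = 0.46, 10% narrower |
| 0.40 | r = −0.24, 2% narrower | r = 0.04, 1% wider | r = 0.37, 6% narrower |
| 0.52 | r = −0.42, 8% narrower | r = −0.13, <1% wider | r = 0.25, 2% narrower |

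So the change for ER runs from about 1% wider to 10% narrower, and r takes either sign.

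**4. Baseline gaps.** Two cohorts of 20 differ by chance in mean baseline with SE √(2/20) = 0.32 baseline SDs. A gap of d SDs moves the unadjusted difference by r × 0.74 × d. At |r| = 0.5 and d = 0.316 that is 0.117 log units, or about 12%. For 400 versus 800 mg this is a component of the variance already counted in step 2.

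**The case against.** The strongest reply is that nothing planned is wrong. The primary objective is the change at each dose, SAP 6.8 specifies no between-dose contrast, and there is no testing. Comparison across doses is descriptive, single-dose means gain least, and baseline values are tabulated so that an imbalance would be visible. All of this stands, and it makes the point one of efficiency. It does not remove the point, because the protocol says that the doses will be compared and the term costs almost nothing.

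Four stronger readings are tempting, and the documents do not support them.

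- A reader might infer that a cohort starting higher will appear to fall more. That holds only if r is negative. For ER the sign is open (step 3).
- A reader might assume equal log-SDs before and on treatment, which gives narrowing of 19%, 13% and 7% for pre/on-treatment correlations of 0.3, 0.5 and 0.7. With the SAP's 0.74, that needs a baseline ER log-SD of 0.74/√(2(1 − ρ)) = 0.63, 0.74 and 0.96. The last exceeds the 0.90 ceiling, and the others are well above the log-uniform 0.52. Those figures do not describe the primary endpoint.
- A reader might count the 12% shift as a bias on top of the wider interval. For the randomised 400 and 800 mg cohorts, chance imbalance is already in the CI, so it is the same effect.
- A reader might infer that the covariate repairs the comparison with 200 mg. With non-randomised groups and a baseline measured with error, neither a change score nor a baseline-adjusted model is guaranteed to be unbiased, and the assumption that would decide between them cannot be tested here.

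The reply is also right that a model change after 400 and 800 mg have closed, in an open-label study with biomarker data read in batches (Protocol 4.4), weakens pre-specification. That stands, and the fix has to answer it.

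**Conclusion.** The omission is confirmed by the model equation, and no other section makes it good. The planned estimates and intervals are valid, and no sample size or error rate is affected. What is lost is precision for differences between doses: about 4%, 13% and 28% of CI width at |r| = 0.3, 0.5 and 0.7, against a cost of about 1% if r = 0. For ER the change is probably between 1% wider and 10% narrower. PR and Ki-67, whose baselines are not restricted by eligibility, may gain more.

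These sizes rest on 20 evaluable patients in each of three cohorts, approximate log-normality, an assumed r, and, for ER, an assumed baseline log-SD of 0.30 to 0.52 inferred from the eligibility rule. That rule is applied to local laboratory results and has an Allred alternative, so the ER range is indicative. Confidence is high that the term is absent and moderate about the size of the gain.

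**What to change.** In SAP 6.8, add the log pre-treatment value of the same biomarker:

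Y = μ + arm + histology + γ·log(pre-treatment value) + error.

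Evaluate each arm's least square mean at the common mean log baseline. Report the currently planned estimate, without the baseline term, alongside it for every biomarker and cohort.

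Settle this in a dated SAP revision before Cohort C biomarker data are analysed. Protocol 9.4.1 allows an analysis change that does not alter a principal feature to be documented in the SAP and study report without a protocol amendment. The SAP still describes every participant as randomised (5.1 and 5.3), so it needs revising for Cohort C in any case.

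Add a sentence on the 200 mg cohort. The adjustment reduces measured baseline differences only, rests on an untestable assumption, and does not remove other differences that come from later, non-randomised enrolment.

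The cost is one residual degree of freedom, no new data, and a late change to a planned model. Showing both results side by side limits the last of these.

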6.9. Safety Analyses

6.9.1. Extent of Exposure

Drug exposure and dose intensity for LY3484356 will be summarized. Drug exposure will include summaries of duration on therapy (in weeks), and cumulative dose. Dose intensity will be calculated as the actual cumulative amount of drug taken divided by the duration of treatment. Relative dose intensity will be calculated as the actual amount of drug taken divided by the amount of drug prescribed times 100% (expressed as a percentage).

6.9.2. Adverse Events

Adverse event (AE) severity grades will be assigned by the investigator using Common Terminology Criteria for Adverse Events (CTCAE) Version 5.0. In addition, AE verbatim text will also be mapped by the sponsor or designee to corresponding terminology within MedDRA.

Preexisting conditions are defined as AEs that either are ongoing at informed consent and or end on or after informed consent. Pre-existing conditions will be included in the listing of AE so that the history of AEs can be traced.

A treatment-emergent adverse event (TEAE) is defined as an AE that first occur or worsen in CTCAE grade after the first dose of study treatment. The MedDRA LLT will be used in the treatment-emergent computation.

The following summaries and listings will be produced:

- Overview of adverse events
- Summary of TEAEs by preferred term (PT) (any grade and Grade ≥ 3)
- Summary of Serious AEs by PT
- Summary of AEs as reason for study treatment discontinuation by PT
- Summary of AEs as reason for surgery delay by PT
- Listing of AEs
- Summary of DLT-equivalent Toxicities
- Listing of DLT-equivalent Toxicities

The TEAE and SAE summaries will be produced for all TEAEs/SAEs and repeated for TEAEs/SAEs related to study treatment, where relationship of the AE to the study treatment will be assessed by the investigator (yes or no).

6.9.3. Deaths and Other Serious Adverse Events

A summary of all deaths, including reasons for deaths, will be provided. All deaths, deaths on study treatment, deaths within 30 days of discontinuation of study treatment, deaths on study treatment or within 30 days of discontinuation of study treatment, and deaths after 30 days of discontinuation of study treatment will be summarized by reason for death. For deaths due to AE, the preferred term will be provided. In addition to the tabular summary, a by-participant listing of all deaths on study not attributed to study disease by the investigator will be provided.

6.9.4. Clinical Laboratory Evaluation

All relevant hematology and chemistry laboratory values will be graded according to CTCAE Version 5. Shift tables showing the change from baseline to the worst grade on study will be summarized. Abnormal laboratory parameters will be listed.

6.9.5. Vital Signs and Other Physical Findings

All vital signs (e.g. temperature, blood pressure, pulse rate, height, weight) will be summarized. A summary of change from baseline in vital sign parameters will also be provided.

6.9.6. *Electrocardiograms*

A summary of single local electrocardiograms (ECGs) will be provided. The summary will classify participants as having normal or abnormal. Adverse events that could be associated with abnormal ECGs will be presented, if appropriate.

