1.3. Schedule of Activities

Screening, On-Study, and Post-Treatment Schedule of Activities						
Screening		On-Treatment		Post-Treatment		
	(Day Relative to Day 1) ≤28	Start of Treatment	Pre-Surgery/Biopsy Visit ^a Within 7 days prior to Surgery/Biopsy	Surgery or Biopsy	Short-term follow-up ^b	
Visit	Screening	V1	V2	V3	V4	Instructions
Procedure						
Informed consent	X					ICF must be signed before any protocol-specific procedures are performed
Inclusion/exclusion criteria	X					
Medical history and description of primary breast cancer	X					
 Complete assessment of prior medical, surgical and social history (such as tobacco and alcohol use). From pathology report, record primary diagnosis, tumor grade, and any additional biomarker testing including receptor status (ER/PR/HER2) and Ki-67 (if reported) from the invasive breast cancer.
Clinical Tumor Measurement	X					Record estimated size of tumor and clinical stage (per AJCC) from pre-operative imaging study (mammogram, MRI or equivalent).
Vital signs	X	X	X		X	Measure vital signs (temperature, blood pressure, pulse rate, and pulse oximetry) may be performed ≤3 days prior to V1. V1&V2 vital signs should be measured before first dose. At V1, vital signs measurement will be also collected 3-4 hours post-dose.

Screening, On-Study, and Post-Treatment Schedule of Activities						
Screening			On-Treatment		Post-Treatment	
	(Day Relative to Day 1) ≤28	Start of Treatment Day 1	Pre-Surgery/Biopsy Visit ^a Within 7 days prior to Surgery/Biopsy	Surgery or Biopsy Day 15 (-2 to +7 days)	Short-term follow-up ^b 30 days post-surgery/biopsy (±14 days)	
Visit	Screening	V1	V2	V3	V4	Instructions
ECOG performance status	X	X	X		X	During study treatment, perform during clinic visits
Physical examination	X	X			X	Collect height and weight at baseline; weight only thereafter
ECG	X	X	X			Single local ECG: V1&V2 ECG should be collected before first dose. At V1, an ECG will also be collected 3-4 hours post-dose. For all visit ECGs, participant should be recumbent or semi-recumbent for 5 to 10 minutes before collection and during study.
Hematology	X	X	X		X	See Appendix 2 (Section 10.2). May be performed ≤3 days prior to V1
Clinical chemistry	X	X	X		X	See Appendix 2 (Section 10.2). May be performed ≤3 days prior to V1
Pharmacokinetics		X	X			See Section 1.3.1 for time points.
Whole blood (PGx)		X				Collect on Day 1/V1 or may be performed ≤3 days prior to V1

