7.1. Discontinuation of Study Intervention

Possible reasons leading to permanent discontinuation of investigational product:

- Subject decision
 - the participant or the participant's designee (eg, parents or legal guardian, requests to discontinue investigational product).
- The patient is significantly noncompliant with study procedures and/or treatment.
- Unacceptable toxicity or DLT toxicity requiring dose discontinuation.
- The patient, for any reason, requires treatment with another therapeutic agent that has been demonstrated to be effective for treatment of the study indication. Discontinuation from study treatment will occur prior to introduction of the new agent.
- The investigator decides that the patient should be discontinued from study treatment.

If a clinically significant finding is identified (including, but not limited to changes from baseline in QT interval corrected using Fridericia's formula) after enrollment, the investigator or qualified designee will determine if the participant can continue in the study and if any change in participant management is needed. This review of the ECG printed at the time of collection must be documented. Any new clinically relevant finding should be reported as an AE.

See the SoA (Section 1.3) for data to be collected at the time of intervention discontinuation and follow-up and for any further evaluations that need to be completed.

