9.4.4. Safety Analyses

All participants who receive at least 1 dose of any study therapy will be evaluated for safety and toxicity.

Safety analyses will include summaries of

- adverse events, including severity and possible relationship to study drug
- serious adverse events, including possible relationship to study drug
- adverse events leading to dose adjustments
- discontinuations from study treatment due to AEs or death
- treatment-emergent abnormal changes in laboratory values, and
- treatment-emergent abnormal changes in vital signs and ECGs.

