6.1.2. Definitions and Conventions

Study treatment refers to LY3484356.

The **date of randomization** is the date the patient was randomly assigned to a study treatment using the IWRS.

The **date of first dose** is the date of the first dose of LY3484356.

The **baseline value of a safety assessment** is the last value observed prior to the first dose of LY3484356.

The **baseline value of an efficacy assessment** is the last value observed prior to the date of enrollment/randomization. If a patient's first assessment occurs after enrollment/randomization but prior to the first dose, this assessment will be used as the baseline.

The **study day of a safety event or assessment** will be calculated as:

- the difference between the date of the event or assessment and the date of first dose plus 1 for all events or assessments occurring on or after the day of first dose. For example, if an event occurs on 08MAR2016 and the date of first dose was 06MAR2016, the study day of the event is 3.
- the difference between the date of the event or assessment and the date of first dose for all events or assessments occurring before the day of first dose. For example, if an event occurs on 05MAR2016 and the date of first dose was 06MAR2016, the study day of the event is -1.

The **study day of an efficacy event or assessment** will be calculated as:

- the difference between the date of the event or assessment and the date of enrollment/randomization plus 1 for all events or assessments occurring on or after the date of randomization.
- the difference between the date of the event or assessment and the date of enrollment/randomization for all events or assessments occurring before the date of randomization.

One **month** is defined as 365/12 days.

Unless otherwise noted, summaries of continuous variables will include a mean, median, standard deviation, minimum, and maximum.

Unless otherwise noted, summaries of categorical variables will include the frequency and percentage (relative to the population being analyzed) of each category.

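### The SAP's ECG summary has no baseline comparison, so it delivers the protocol's treatment-emergent ECG summary only for clinically significant findings reported as adverse events

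*SAP*

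**What the plan says.** SAP 6.9.6 (Electrocardiograms) has three sentences. The first gives the data source: "A summary of single local electrocardiograms (ECGs) will be provided". The second gives the rule: "The summary will classify participants as having normal or abnormal". The third adds a conditional item: "Adverse events that could be associated with abnormal ECGs will be presented, if appropriate". None of them mentions baseline, visit, time point, interval values or cohort.

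Protocol 9.4.4 includes "treatment-emergent abnormal changes in vital signs and ECGs" in the list of safety summaries. Protocol 7.1 gives "changes from baseline in QT interval corrected using Fridericia's formula" as an example of a clinically significant finding that the investigator must assess.

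The Schedule of Activities (Protocol 1.3) places ECGs at screening, V1 and V2. On timing it says "V1&V2 ECG should be collected before first dose" and "At V1, an ECG will also be collected 3-4 hours post-dose". I read the V2 instruction as before that day's dose, since V2 falls during treatment.

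SAP 6.1.2 defines the baseline of a safety assessment: it "is the last value observed prior to the first dose of LY3484356". SAP 6.9.4 uses a baseline comparison for laboratory grades (shift to worst grade), and SAP 6.9.5 uses one for vital signs (change from baseline). SAP 6.9.6 does not.

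**The concern.** A participant-level label of normal or abnormal describes a state, and the protocol promises a summary of changes. Without the pre-dose reading beside it, the label mixes pre-existing abnormality with abnormality that arose on drug. Pre-existing abnormality is possible in this population, because exclusion 21(f) in Protocol 5.2 exempts rate-controlled atrial fibrillation.

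Safety and tolerability at each dose level is a secondary objective, and the cohorts run from 200 to 800 mg. If the ECG table cannot separate old findings from new ones, a reader of the study report learns little from comparing it across cohorts. The label also carries no magnitude, so the one ECG quantity that Protocol 7.1 singles out, QTcF change from baseline, has no planned summary.

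**Working it through.** Neither document states an ECG or QTcF figure (no SD, margin or expected rate), so there is nothing to reproduce. The check is a comparison of texts.

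1. **What the protocol summary needs.** To call an ECG change treatment-emergent, each participant needs a pre-dose reading, a reading on drug, and a rule comparing them.

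2. **Whether the readings are scheduled.** They are. Before the first dose there are the screening ECG and the V1 pre-dose ECG. On drug there are the V1 ECG at 3-4 hours post-dose and the V2 ECG. Only the first of these is strictly post-dose; V2 is on treatment but before that day's dose.

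3. **Whether a baseline is defined.** It is. SAP 6.1.2 applies to any safety assessment. For ECGs it gives the V1 pre-dose reading, or the screening reading if V1 pre-dose is missing.

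4. **Whether SAP 6.9.6 compares the two.** It does not. It does not say which ECGs feed the label:
   - If all ECGs count, an abnormal screening ECG alone makes the participant abnormal.
   - If only on-drug ECGs count, a persistent pre-dose abnormality still makes the participant abnormal.
   - Either way, the case that was abnormal before dosing and the case that became abnormal on drug fall in the same cell.

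5. **How the SAP treats its other safety data.**
   - Laboratory values (6.9.4): shift from baseline to worst grade.
   - Vital signs (6.9.5): change from baseline.
   - ECGs (6.9.6): normal or abnormal, with no baseline.

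6. **What reaches the report by another route.** Protocol 7.1 and Appendix 3 (10.3.1) make new clinically relevant ECG findings, and clinically significant abnormalities that worsen from baseline, adverse events. SAP 6.9.2 tabulates events that first occur or worsen after the first dose. So clinically significant treatment-emergent ECG findings are covered. Shifts not judged clinically significant, and QTcF magnitude, are not.

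7. **Illustration only.** The documents give no rate of abnormal ECGs before dosing. Assume 10% to 30%, persisting on study, with about 30 participants per cohort (Protocol 1.1). The label would then count 30 × 0.10 = 3 to 30 × 0.30 = 9 participants per cohort as abnormal with no drug effect at all. A shift table would put them in the abnormal-to-abnormal cell.

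**The case against.** The strongest reply is that the protocol's commitment is already met. Protocol 9.4.4 promises treatment-emergent abnormal changes, not QTcF means, and the adverse event route in step 6 captures those that matter clinically. SAP 6.9.6 is silent on visits but does not forbid a by-visit table. SAP 6.1 allows further exploratory analyses, and SAP 6.13 leaves PK/PD methods to a separate document. This is a short Phase 1 biomarker study with no formal hypothesis testing.

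Much of this stands, and it limits the point. It does not remove it. Protocol 9.4.4 lists ECG changes as a summary separate from adverse events. The adverse event route depends on a judgement of clinical significance, and the ECG-related listing in SAP 6.9.6 is conditional. Permission for unspecified analyses is not a plan for this one.

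A reader might also infer more than the documents support:

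- **That a heart-rate trend would be missed.** It would not. SAP 6.9.5 lists pulse rate and plans change from baseline. The Schedule of Activities takes vital signs at V1 before dosing and 3-4 hours after, and at V2, which are the ECG time points.
- **That the trial cannot show a QTcF effect.** The limit lies in the planned summary, not in the scheduled recordings. The documents also do not establish that QTcF values after baseline are entered in the database.
- **That the loss can be stated as power, or as a count above 470 msec.** The documents give no QTcF SD. The 470 msec value is an entry exclusion in Protocol 5.2, not the SAP's definition of abnormal.
- **That a QTcF table would settle a dose relationship.** The ECGs are single and local, and there is no placebo. The 200 mg cohort is not randomised and opens after the other two close (Protocol 6.3).

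**Conclusion.** The point holds in a limited form. The ECG summary in SAP 6.9.6 has no baseline comparison, so by itself it does not deliver the treatment-emergent ECG summary in Protocol 9.4.4. The part that is delivered, through adverse event reporting, is the clinically significant part. The gap is shifts below that threshold and the magnitude of QTcF change, which Protocol 7.1 treats as worth attention.

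The point is minor. It affects one descriptive table under a secondary objective, has no bearing on the ER, PR or Ki-67 analyses, and changes no sample size or error rate. The conclusion rests on reading SAP 6.9.6 as the full plan for ECG tables; no other SAP section specifies one. It does not rest on the illustration in step 7, whose rates are assumed.

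**What to change.** In SAP 6.9.6, replace the single normal/abnormal count with a shift table by cohort in the safety population. Shift from baseline (SAP 6.1.2) to the worst post-baseline ECG category, using the V1 3-4 hour post-dose ECG and the V2 ECG. Label V2 as on treatment, before that day's dose. Include all three dose cohorts.

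Where QTcF values are captured, add a descriptive summary of QTcF change from baseline at those two time points by cohort, with a confidence interval (the SAP 6.1 default is two-sided 95%). Note beside it that single local ECGs, no placebo and a non-randomised 200 mg cohort limit any inference about dose.

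A shift table cannot show a new abnormality in a participant already abnormal at baseline, so keep the presentation of ECG-related adverse events beside it.

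The cost is SAP wording and one or two tables from ECGs already scheduled, with no new procedure. The shift table needs only the normal/abnormal reading at each time point. The QTcF summary needs data entry if the values are not already in the database, and the documents do not say whether they are.
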